5.0 Data Management and Analysis

5.1 Outcome Measures and Data Analysis Plan

5.2 Change in NRS pain score from baseline will be analyzed for pre and post-treatment each treatment day throughout the study, and WOMAC (pain, stiffness, and functional change) will be evaluated on day 1 and day 7. Data will be analyzed using t-tests and repeated measure ANOVAs.

6.0 Risk Analysis

6.1 Adverse Event Recording and Reporting

6.1.1 Adverse Event Definitions

Adverse effect. Any untoward medical occurrence in a clinical study of an investigational device; regardless of the causal relationship of the problem with the device or, if applicable, other study treatment or diagnostic product(s).

Associated with the investigational device or, if applicable, other study treatment or diagnostic product(s). There is a reasonable possibility that the adverse effect may have been caused by the investigational device or, if applicable, the other study treatment or diagnostic product(s).

Disability. A substantial disruption of a person's ability to conduct normal life functions.

Life-threatening adverse effect. Any adverse effect that places the subject, in the view of the investigator-sponsor, at immediate risk of death from the effect as it occurred (i.e., does not include an adverse effect that, had it actually occurred in a more severe form, might have caused death).

Serious adverse effect. Any adverse effect that results in any of the following outcomes: death, a life-threatening adverse effect, inpatient hospitalization or prolongation of existing hospitalization, a persistent or significant disability/incapacity, or a congenital anomaly/birth defect.

Unexpected adverse effect. Any adverse effect, the frequency, specificity or severity of which is not consistent with the risk information described in the clinical study protocol(s)

Unanticipated adverse device effect. Any serious adverse effect on health or safety or any life-threatening problem or death caused by, or associated with, a device, if that effect, problem, or death was not previously identified in nature, severity, or degree of incidence in the investigational plan or IDE application (including a supplementary plan or application), or any other unanticipated serious problem associated with a device that relates to the rights, safety, or welfare of subjects.

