1.4 Potential Risks to Subjects

The risks of using ultrasound devices to administer physical therapy are well established and include: burn, itching and/or pain. These risks decrease when using lower intensity ultrasound, as in this study. The Ultrasound Diathermy Device uses existing technology to deliver ultrasound therapy in a portable and convenient fashion. The subjects will be given the chance to ask any questions regarding the trial procedures, requirements, and purposes. Once the subjects are fully informed of the possible risks and benefits of participation in the study and all of their questions have been satisfactorily answered, they will be required to sign the informed consent form in order to participate in the study. All subjects must give consent themselves and no legally authorized representatives will be accepted on their behalf.

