6.1.4 Reporting of Adverse Effects to the FDA

The investigator-sponsor will submit a completed Form FDA 3500 A to the FDA's Center for Devices and Radiological Health for any observed or volunteered adverse effect that is determined to be an *unanticipated adverse device effect*. A copy of this completed form will be provided to all participating sub-investigators.

The completed Form FDA 3500 A will be submitted to the FDA as soon as possible and, in no event, later than 10 working days after the investigator-sponsor first receives notice of the adverse effect.

If the results of the sponsor-investigator's follow-up evaluation show that an adverse effect that was initially determined to not constitute an *unanticipated adverse device effect* does, in fact, meet the requirements for reporting; the investigator-sponsor will submit a completed Form FDA 3500 A as soon as possible, but in no event later than 10 working days, after the determination was made.

For each submitted Form FDA 3500 A, the sponsor-investigator will identify all previously submitted reports that that addressed a similar adverse effect experience and will provide an analysis of the significance of newly reported adverse effect in light of the previous, similar report(s).

Subsequent to the initial submission of a completed Form FDA 3500 A, the investigator-sponsor will submit additional information concerning the reported adverse effect as requested by the FDA.

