6.1.5 Reporting of Adverse Effects to the Responsible IRB

In accordance with applicable policies of the Institutional Review Board (IRB), the investigator-sponsor will report, to the IRB, any observed or volunteered adverse effect that is determined to meet all of the following criteria: 1) associated with the investigational device or, if applicable, other study treatment or diagnostic

product(s); 2) a serious adverse effect; and 3) an unexpected adverse effect. Adverse event reports will be submitted to the IRB in accordance with the respective IRB procedures.

Applicable adverse effects will be reported to the IRB as soon as possible and, in no event, later than 10 calendar days following the investigator-sponsor's receipt of the respective information. Adverse effects which are 1) associated with the investigational drug or, if applicable, other study treatment or diagnostic product(s); 2) fatal or life-threatening; and 3) unexpected will be reported to the IRB within 24 hours of the investigator-sponsor's receipt of the respective information.

Follow-up information to reported adverse effects will be submitted to the IRB as soon as the relevant information is available. If the results of the sponsor-investigator's follow-up investigation show that an adverse effect that was initially determined to not require reporting to the IRB does, in fact, meet the requirements for reporting; the investigator-sponsor will report the adverse effect to the IRB as soon as possible, but in no event later than 10 calendar days, after the determination was made.

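### The closed list of serious outcomes omits injury needing treatment to prevent permanent damage, so a deep burn treated without admission or significant disability falls outside the IRB rule and reaches the FDA only through an undefined term

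*Combined protocol and SAP*

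**What the plan says.** **Seriousness.** Section 6.1.1 of the combined protocol and SAP calls an adverse effect serious if it results in one of five outcomes: "death, a life-threatening adverse effect, inpatient hospitalization or prolongation of existing hospitalization, a persistent or significant disability/incapacity, or a congenital anomaly/birth defect". There is no item for other medically important events, and no other section adds an outcome. The same section defines disability as "A substantial disruption of a person's ability to conduct normal life functions".

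**Named risk.** Section 1.4 says that the risks of therapeutic ultrasound devices "are well established and include: burn, itching and/or pain". It gives no depth or grade of burn, and adds that risk is lower at the intensity used here.

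**IRB rule.** Section 6.1.5 requires a report, within 10 calendar days, of an effect that is associated with the device and is also "2) a serious adverse effect; and 3) an unexpected adverse effect". All three conditions must hold. A separate 24-hour route applies to associated, unexpected effects that are fatal or life-threatening.

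**FDA rule.** Section 6.1.4 requires a form, within 10 working days, "for any observed or volunteered adverse effect that is determined to be an" unanticipated adverse device effect. Section 6.1.1 defines that term in two parts. The first is "Any serious adverse effect on health or safety or any life-threatening problem or death caused by, or associated with, a device", provided that it "was not previously identified in nature, severity, or degree of incidence in the investigational plan or IDE application". The second is a catch-all: "or any other unanticipated serious problem associated with a device that relates to the rights, safety, or welfare of subjects".

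**Review steps.** Section 6.1.3.1 has the investigator-sponsor decide three things: whether an abnormal finding is an adverse effect, whether the device may have caused it, and whether it meets the criteria for a serious adverse effect.

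**The concern.** Subjects treat themselves outside the clinic, 4 hours a day for 5 to 7 days (Sections 3.3 and 4.3.1). A local burn managed as an outpatient is a foreseeable form of a harm that the protocol itself names, and it can threaten lasting local damage without disrupting normal life. The list of serious outcomes has no item suited to it.

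What is at stake is timely outside review. Section 6.1.3 records every adverse effect, but recording carries no deadline. Monitoring under Section 7.0 may be as rare as once a year, while enrollment is planned over 2 months (Section 4.1). Without a time-limited report, the IRB might not learn of such a burn while the study is running.

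**Working it through.** There is no planned figure to reproduce. The check traces one case through the definitions and rules: a deep device burn that needs medical or surgical care to prevent permanent damage, is treated without admission, and causes no significant disability or incapacity.

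**Step 1. Is it serious under Section 6.1.1?**

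| Listed outcome | This burn |
|---|---|
| Death | No |
| Life-threatening | No |
| Admission or prolonged stay | No, treated without admission |
| Persistent or significant disability/incapacity | No, by the terms of the case |
| Congenital anomaly or birth defect | No |

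None of the five applies, so the burn is non-serious by definition.

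**Step 2. Does it reach the IRB under Section 6.1.5?** The ordinary route needs associated, serious and unexpected. The second condition fails, so the route is closed whatever the answer on the other two. The 24-hour route needs a fatal or life-threatening effect and is also closed. The rule has no catch-all.

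**Step 3. Does it reach the FDA under Section 6.1.4?** The first part of the unanticipated adverse device effect definition needs a serious adverse effect, a life-threatening problem or death, so it fails. The catch-all speaks of a serious problem, which is not the defined term and is not tied to the five outcomes. A deep burn judged unanticipated could be reported under it. But the protocol does not say what a serious problem is, and none of the three decisions in Section 6.1.3.1 leads a reviewer to ask. The FDA route is open but uncertain.

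**Step 4. Would adding the outcome be enough?** The burn would become serious. The IRB rule would still need it to be unexpected, and the first part of the FDA definition would still need it not to have been identified in nature, severity or incidence. Section 1.4 names burn without a severity. One reader could say that any burn is expected; another could say that a deep burn goes beyond what was described. Severity is a ground in both definitions, so stating the expected severity would settle the question.

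**Exposure, for context only.** Section 3.2 plans 35 enrolled and 30 completers. Section 4.3.1 gives 4 hours a day for 5 to 7 days.

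- Hours per subject: 4 × 5 = 20 to 4 × 7 = 28.
- All 35 complete the schedule: 35 × 20 = 700 to 35 × 28 = 980 hours.
- 30 completers only: 30 × 20 = 600 to 30 × 28 = 840 hours.

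These are hours of exposure. With no burn rate in the documents they do not convert into expected events, and the point does not depend on them.

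**The case against.** The strongest reply is that little is lost. The catch-all can carry a deep burn to the FDA. The disability outcome need be only significant, not persistent, and incapacity is undefined, so a knee burn in an ambulatory subject may well qualify. All effects are recorded, device-associated ones are followed until they resolve or stabilize, and the investigator-sponsor must review them promptly. IRB reports also follow the IRB's own policies, which are not in the documents and may reach further. The documents supply no standard that requires a sixth outcome.

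Much of this stands, and it rules out several stronger readings that a reader might infer:

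- *That the burn necessarily misses the FDA rule.* The catch-all is not limited to the five outcomes.
- *That every burn treated without admission is non-serious.* Some would meet the disability or incapacity outcome.
- *That the most severe burns escape.* Burns leading to admission, significant disability or danger to life are already serious. The gap concerns an intermediate grade.
- *That enrollment would otherwise continue unchecked.* Sections 6.1.4 and 6.1.5 set reporting duties and do not link a report to pausing enrollment.
- *That adding the outcome alone makes the other sections work.* Step 4 shows that it does not.

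The reply does not close the gap in the IRB rule as written, and it does not supply a meaning for a serious problem or a step that leads to it.

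**Conclusion.** The concern holds in a limited form. For a deep device burn treated without admission and without significant disability or incapacity, the closed list gives the answer non-serious, and the IRB rule as written then requires no report. The FDA report depends on an undefined term outside the listed review steps.

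In practical terms, one class of injury cannot reach the 10-calendar-day IRB report and has only an uncertain route to the 10-working-day FDA report. Even if it were classed as serious, the IRB report and the first part of the FDA definition would apply only to a burn that is also device-associated and counted as unexpected or not previously identified.

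This rests on two assumptions: that the list is read as closed, as its wording indicates, and that the IRB's own procedures add nothing. Whether an outside regulation requires the missing outcome cannot be judged from these documents and plays no part here. The change should be made: the stated list would misclassify a foreseeable event.

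**What to change.** Make two changes together.

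1. In Section 6.1.1, add a sixth outcome to the definition of a serious adverse effect: *or requires medical or surgical intervention to prevent permanent impairment of a body function or permanent damage to a body structure*.
2. In Section 1.4, state what severity of burn counts as expected, so that a more severe burn is clearly unexpected for the IRB rule and not previously identified in severity for the FDA rule. The sponsor should set that level.

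With both in place, a device-associated burn of this kind that exceeds the stated severity meets the conditions of Sections 6.1.4 and 6.1.5, and no longer depends on the undefined catch-all.

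The cost is one clause, one sentence, and a matching entry wherever seriousness is recorded. The downside is that an occasional extra event will be classed as serious and reported. The change concerns classification and reporting only and leaves treatment of subjects as it is.

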6.1.2 Eliciting Adverse Effect Information

Clinical study subjects will be routinely questioned about adverse effects at study visits.

6.1.3 Recording and Assessment of Adverse Effects

All observed or volunteered adverse effects (serious or non-serious) and abnormal test findings, regardless of treatment group, if applicable, or suspected causal relationship to the investigational device or, if applicable, other study treatment or diagnostic product(s) will be recorded in the subjects' case histories. For all adverse effects, sufficient information will be pursued and/or obtained so as to permit 1) an adequate determination of the outcome of the effect (i.e., whether the effect should be classified as a serious adverse effect) and; 2) an assessment of the casual relationship between the adverse effect and the investigational device or, if applicable, the other study treatment or diagnostic product(s).

Adverse effects or abnormal test findings felt to be associated with the investigational device or, if applicable, other study treatment or diagnostic product(s) will be followed until the effect (or its sequelae) or the abnormal test finding resolves or stabilizes at a level acceptable to the investigator-sponsor.

6.1.3.1 Causality and Severity Assessment

The investigator-sponsor will promptly review documented adverse effects and abnormal test findings to determine 1) if the abnormal test finding should be classified as an adverse effect; 2) if there is a reasonable possibility that the adverse effect was caused by the investigational device or, if applicable, other study treatment or diagnostic

product(s); and 3) if the adverse effect meets the criteria for a serious adverse effect.

If the investigator-sponsor's final determination of causality is "unknown and of questionable relationship to the investigational device or, if applicable, other study treatment or diagnostic product(s)", the adverse effect will be classified as associated with the use of the investigational device or study treatment or diagnostic drug product(s) for reporting purposes. If the investigator-sponsor's final determination of causality is "unknown but not related to the investigational device or, if applicable, other study treatment or diagnostic product(s)", this determination and the rationale for the determination will be documented in the respective subject's case history.

6.1.4 Reporting of Adverse Effects to the FDA

The investigator-sponsor will submit a completed Form FDA 3500 A to the FDA's Center for Devices and Radiological Health for any observed or volunteered adverse effect that is determined to be an *unanticipated adverse device effect*. A copy of this completed form will be provided to all participating sub-investigators.

The completed Form FDA 3500 A will be submitted to the FDA as soon as possible and, in no event, later than 10 working days after the investigator-sponsor first receives notice of the adverse effect.

If the results of the sponsor-investigator's follow-up evaluation show that an adverse effect that was initially determined to not constitute an *unanticipated adverse device effect* does, in fact, meet the requirements for reporting; the investigator-sponsor will submit a completed Form FDA 3500 A as soon as possible, but in no event later than 10 working days, after the determination was made.

For each submitted Form FDA 3500 A, the sponsor-investigator will identify all previously submitted reports that that addressed a similar adverse effect experience and will provide an analysis of the significance of newly reported adverse effect in light of the previous, similar report(s).

Subsequent to the initial submission of a completed Form FDA 3500 A, the investigator-sponsor will submit additional information concerning the reported adverse effect as requested by the FDA.

6.1.5 Reporting of Adverse Effects to the Responsible IRB

In accordance with applicable policies of the Institutional Review Board (IRB), the investigator-sponsor will report, to the IRB, any observed or volunteered adverse effect that is determined to meet all of the following criteria: 1) associated with the investigational device or, if applicable, other study treatment or diagnostic

product(s); 2) a serious adverse effect; and 3) an unexpected adverse effect. Adverse event reports will be submitted to the IRB in accordance with the respective IRB procedures.

Applicable adverse effects will be reported to the IRB as soon as possible and, in no event, later than 10 calendar days following the investigator-sponsor's receipt of the respective information. Adverse effects which are 1) associated with the investigational drug or, if applicable, other study treatment or diagnostic product(s); 2) fatal or life-threatening; and 3) unexpected will be reported to the IRB within 24 hours of the investigator-sponsor's receipt of the respective information.

Follow-up information to reported adverse effects will be submitted to the IRB as soon as the relevant information is available. If the results of the sponsor-investigator's follow-up investigation show that an adverse effect that was initially determined to not require reporting to the IRB does, in fact, meet the requirements for reporting; the investigator-sponsor will report the adverse effect to the IRB as soon as possible, but in no event later than 10 calendar days, after the determination was made.

7.0 Monitoring Procedures

Monitoring of the clinical study for clinical protocol compliance will be conducted periodically (i.e., at a minimum of annually) by the clinical team. The sponsor-investigator will permit direct access to the study monitors and appropriate regulatory authorities to the study data and to the corresponding source data and documents to verify the accuracy of these data.

8.0 Additional Records and Reports

8.1 Data Handling and Record-keeping

A Case Report Form (will be completed at each study visit for each subject enrolled into the clinical study. The investigator-sponsor will review, approve and sign/date each completed CRF; the investigator-sponsor's signature serving as attestation of the investigator-sponsor's responsibility for ensuring that all clinical and laboratory data entered on the CRF are complete, accurate and authentic.

The clinical research team will work with each site to ensure accurate completion of CRFs reconciling illegible entries, missing data, and conflicting data entries.

Source Data are the clinical findings and observations, laboratory and test data, and other information contained in Source Documents. Source Documents are the original records (and certified copies of original records); including, but not limited to, hospital medical records, physician or office charts, physician or nursing notes, subject diaries or evaluation

checklists, pharmacy dispensing records, recorded data from automated instruments, x-rays, etc. When applicable, information recorded on the CRF shall match the *Source Data* recorded on the *Source Documents*.

8.2 Record Maintenance and Retention

The investigator-sponsor will maintain records in accordance with Good Clinical Practice guidelines; to include:

- IRB correspondence (including approval notifications) related to the clinical protocol; including copies of adverse event reports and annual or interim reports;
- Current and past versions of the IRB-approved clinical protocol and corresponding IRB-approved consent form(s) and, if applicable, subject recruitment advertisements.
- Signed Investigator's Agreements and Certifications of Financial Interests of Clinical Investigators;
- Curriculum vitae (investigator-sponsor and clinical protocol subinvestigators);
- Certificates of required training (e.g., human subject protections, Good Clinical Practice, etc.) for investigator-sponsor and listed subinvestigators;
- Instructions for on-site preparation and handling of the investigational device and/or study treatment or diagnostic product(s), and other studyrelated materials (i.e., if not addressed in the clinical protocol);
- Decoding procedures for blinded trials;
- Master device list;
- Signed informed consent forms:
- Completed Case Report Forms; signed and dated by investigatorsponsor:
- Source Documents or certified copies of Source Documents;
- Monitoring visit reports;
- Copies of investigator-sponsor correspondence to sub-investigators, including notifications of adverse effect information;
- Subject screening and enrollment logs;
- Subject identification code list;
- Device accountability records, including documentation of device disposal and returns to sponsor;
- Final clinical study report.

Site-subject identification numbers will be assigned to all subjects to deidentify the associated clinical data. A master subject ID log will be maintained by research coordinator separately from clinical trial data. The master log will contain the assigned site-subject identification number matched to each subject's full name, gender, and date-of-birth. The sitesubject ID will be generated by a two-digit site ID separated by a dash from the subject number at that site. Subjects' names or other directly identifiable information will not be used in any reports, publication or other disclosures of clinical study outcomes. The investigator-sponsor will retain the specified records and reports for up to 2 years after the marketing application is approved for the investigational device; or, if a marketing application is not submitted or approved for the investigational drug, until 2 years after investigations under the IDE have been discontinued and the FDA so notified.

